2. The perioperative use of Dsuvia (sufentanil SL) will be associated with lower overall opioid consumption, lower frequency of rescue opioids, lower PACU and hospital length of stay, and fewer side effects of opioid use (i.e., nausea, vomiting, constipation, respiratory complications) than observed in two historical control groups of patients receiving remifentanil or sufentanil infusions without perioperative Dsuvia.

Methods:

The study design is an Observational Longitudinal (OL) study with historical controls. There will be 1 prospectively recruited study arm (patients receiving the study drug Dsuvia) and 2 historical control arms (one that received an intraoperative remifentanil infusion and the other that received an intraoperative sufentanil infusion, both without Dsuvia).

Inclusion criteria:

[figure not shown]
Patients undergoing spine surgery (1-3 levels) who are opioid-naïve (no opioid use 30 days prior to surgery), 18-75 years old, ASA physical status 1-3.

Exclusion criteria:

Microdiscectomy, chronic opioid users, significant respiratory depression, acute or severe bronchial asthma, chronic lung disease, known or suspected gastrointestinal obstruction including paralytic ileus, liver disease (defined as alkaline phosphatase (ALP) > 56, aspartate aminotransferase (AST) > 100), known allergy or hypersensitivity to sufentanil or its components, baseline dementia, serotonin syndrome, adrenal insufficiency, severe hypotension, increased intracranial pressure, brain tumors, head injury, impaired consciousness, malignant hyperthermia, ASA physical status > 3, age > 75, pregnant patients.

IV. STUDY SCHEMA:

Patients undergoing spine surgery (1 or more levels)

Dsuvia 30mcg SL

Intraoperative Phase

General endotracheal anesthesia (TIVA with propofol/sufentanil)

Standardized anesthetic technique (see protocol below)

Dsuvia x1 prior to emergence from anesthesia

Postoperative Phase

Pain scores (NRS) q15 min up to 2 hrs

Concomitant Medication use/opioid consumption

Dsuvia prn q1hr as 1st line (NRS >3); Fentanyl prn as 2nd line, or 1st

line if repeat Dsuvia cannot yet be given and NRS is >3 (see PACU schema below)

Up to 3 doses of Dsuvia may be administered in the PACU (each at least 1 hr apart)

Hospitalization Phase

Follow up during inpatient hospital stay

Concomitant Medication use/pain scores

Both arms: standard of care analgesia (PO and IV prn)

Quality of Recovery (QoR); patient satisfaction (study arm only)

Post-discharge Phase

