questions on a 24 hour basis. It will be explained to the patient that they will be permitted to withdraw from the study at any time for any reason until their day of surgery. On arrival at the preoperative area, the patient will be assigned a code by one of the investigators. Prior to premedication, all patients will be made familiar with the use of numeric rating scale (NRS): 0-10 (no pain to the worst pain imaginable). The baseline NRS score will be recorded. All routine standard practices for surgery, anesthesia, and perioperative care will be followed with the exception of the study intervention. All patients will be premedicated with midazolam (0.025-0.05 mg/kg)

Intraoperative Management:

The Study arm will receive general endotracheal anesthesia (GETA). Anesthesia induction will be achieved with propofol (1.5-2.5mg/kg), succinylcholine (1mg/kg), and Fentanyl (50-100 mcg) bolus. Anesthesia maintenance will consist of TIVA (total intravenous anesthesia) with continued infusions of propofol (80-200 mcg/kg/min) and sufentanil (0.2-0.3mcg/kg/hr). The study group will receive Dsuvia 30 mcg at surgery end, administered by the anesthesiologist, timed to occur prior to emergence from anesthesia, and after the patient is turned supine. Antiemetic prophylaxis will be administered (ondansetron) per standard practice. The patient will then be transferred to the PACU.

Postoperative Management:

Note that Dsuvia will be ordered as q1hr prn, meaning that repeat doses must be administered at least 1 hr apart (up to 3 doses can be administered in the PACU).

Postoperative pain scores will be recorded by the PACU nurse and the research assistant. This will be obtained by using NRS scale every 15 mins up to 2 hours.

In the PACU, patients will be ordered to receive Dsuvia 30 mcg q1 hr prn for breakthrough pain (for NRS > 3) as the 1st line analgesic, with fentanyl as the rescue analgesic if the patient is still experiencing pain (NRS >3). The following opioid administration schema will be used for pain management in the PACU:

- 1st line: Dsuvia SL 30mcg (NRS >3). 2nd line: Fentanyl 25-50mcg (NRS >3)
- If upon arrival to the PACU the patient is still experiencing pain with NRS >3 but cannot yet receive a repeat dose of Dsuvia (because of having received 1st dose in the OR less than 1 hour ago), then the patient can receive fentanyl 25-50mcg prn until eligible to receive Dsuvia.

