- If at any time the patient's NRS >3 after 20 min following an administration of either Dsuvia or fentanyl, the patient can receive a repeat dose of fentanyl until again eligible to receive Dsuvia.

Once the patient is transferred to the floor, both groups will receive the standard of care postoperative pain management orders (ie PO and IV prn analgesia for NRS > 3).

Patients who require additional doses of Dsuvia will be monitored for respiratory depression for at least one hour after the last administration of the drug dose.

Sample Size/Statistical analysis:

The primary outcome is nurse-collected mean pain scores. Assuming a within-group standard deviation in PACU NRS pain score of 2.5 points⁷, enrollment of 30 patients in the study group and inclusion of at least 80 patients in each retrospective control group will provide at least 80% power at a two sided alpha level of 0.025 (0.05/2 pair-wise comparisons) to detect a minimal clinically important difference of 2 points⁹ between the Study group and each of the retrospective groups using linear regression.

To account for any potential lack of comparability in baseline characteristics between patients in the Study and retrospective groups, all outcomes will be compared between the prospective group and each of the retrospective groups using doubly robust estimation incorporating both multivariable linear regression adjustment and inverse probability of treatment weights based on the propensity score¹⁰. Doubly robust estimation will allow for unbiased treatment effect estimates even if one of the two models (i.e., propensity score model or outcome model) is miss-specified. The multivariable linear regression models for the outcomes will adjust for the following covariates: age, sex, BMI, ASA class, surgical invasiveness tier, reoperation, history of anxiety, anxiolytic use, history of depression, and antidepressant use. Analytic weights will be based on the inverse of the propensity score, calculated via logistic regression as the probability of being in the Dsuvia group conditional upon the aforementioned covariates included in the multivariable outcome model.

Investigator Name/Institution:

[name], MS
Associate Professor of Anaesthesia
Director, Neuroanesthesia

Brigham and Women's Hospital
Harvard Medical School
Department of Anesthesiology, Perioperative and Pain Medicine
[name]
[name]
[contact]
Email: [contact]

Senior Project Manager:
[name]
Email: [contact]

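### Baseline NRS is recorded in the prospective arm but is in neither adjustment model, and the plan does not say whether historical controls have a comparable score

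*Combined protocol and SAP*

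**What the plan says.** All references are to the combined protocol and SAP.

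- **Methods:** "The study design is an Observational Longitudinal (OL) study with historical controls". There is one prospective Dsuvia arm and two historical control arms, with no randomisation.
- **Detailed Clinical Protocol, Preoperative:** "Prior to premedication, all patients will be made familiar with the use of numeric rating scale (NRS): 0-10", and then "The baseline NRS score will be recorded". This is done after consent and coding on arrival for surgery, so the procedure cannot produce a score for a past patient. The same section has surgeons pick out patients they think could be helped by Dsuvia.
- **Outcomes:** the primary outcome is the mean pain score in the PACU, on the same scale.
- **Sample Size/Statistical analysis:** the purpose of adjustment is given as "To account for any potential lack of comparability in baseline characteristics between patients in the Study and retrospective groups". The outcome model adjusts for "age, sex, BMI, ASA class, surgical invasiveness tier, reoperation, history of anxiety, anxiolytic use, history of depression, and antidepressant use". The propensity score is "conditional upon the aforementioned covariates included in the multivariable outcome model". The robustness claim begins "Doubly robust estimation will allow for unbiased treatment effect estimates even if one of the two models" and concerns misspecification of one model.
- **Study Schema, Hospitalization Phase:** one line reads "Quality of Recovery (QoR); patient satisfaction (study arm only". Baseline NRS is not classified as study-arm only or as available in all groups.

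The plan gives no rule for missing baseline scores and no sensitivity analysis for unmeasured confounding.

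**The concern.** In a comparison with historical controls, the eligibility limits and covariate adjustment are the only protection against groups that differed beforehand. The preoperative value of the outcome scale is an obvious candidate for adjustment, and the team already collects it in one arm. Followed as written, the plan leaves it out even if the control charts turn out to hold it.

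Double robustness gives two chances to model the listed covariates correctly. It does not help with a confounder that is on neither list. If study patients start with less residual pain than controls, the estimate is tilted towards Dsuvia; if they start with more, a real benefit is partly hidden. A reader of the results could not tell which applies, or how large a difference would change the conclusion.

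**Working it through.** **1. The plan's own figure.** Inputs from Sample Size/Statistical analysis: 30 study patients, at least 80 per control group, SD 2.5, difference 2, two-sided alpha 0.025 per comparison (critical value 2.241).

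- Standard error = 2.5 × √(1/30 + 1/80) = 0.535.
- Power = Φ(2/0.535 − 2.241) = 93.3% (92.7% by the noncentral t with 108 df).

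This agrees with the stated lower bound of 80%. It ignores any variance added by weighting.

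**2. Is baseline NRS in either model?** The ten listed covariates contain no measure of preoperative pain. The propensity model takes its covariates from that list, so the omission is common to both.

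**3. Form of the bias.** Bias = (slope of PACU NRS on baseline NRS, given the ten covariates) × (difference in baseline NRS left after those covariates). Neither factor is in the documents.

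A simulation with assumed inputs shows how this works: 4,000 datasets per scenario, 30 vs 80, weighted linear regression, all ten covariates shifted by 0.2 SD between groups and explaining 20% of baseline NRS variance.

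| Residual difference | Slope | Raw difference | Bias, NRS omitted | Bias, NRS in both models |
|---|---|---|---|---|
| 0 | 0.4 | 0.71 | 0.00 | not reported |
| 0.5 | 0.3 | 1.20 | 0.15 | 0.01 |
| 1.0 | 0.4 | 1.72 | 0.40 | 0.01 |
| 1.5 | 0.5 | 2.20 | 0.74 | −0.01 |

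The bias follows the residual difference, not the raw one. In the first row the covariates absorb a raw difference of 0.71 completely.

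**4. How much bias would matter.** Tipping-point bias = observed difference − 2.241 × standard error. The SD of the weighted estimate with NRS omitted was 0.54 to 0.57 at a 0.2 SD covariate shift and 0.63 to 0.66 at 0.35 SD. For an observed 2 points:

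- SD 0.54: 2 − 1.21 = 0.79
- SD 0.57: 2 − 1.28 = 0.72
- SD 0.63: 2 − 1.41 = 0.59
- SD 0.66: 2 − 1.48 = 0.52

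Dividing 0.52 to 0.79 by an assumed slope gives the residual baseline difference needed: 1.04 to 1.58 points at slope 0.5, and 1.74 to 2.63 at slope 0.3.

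**5. Could the study arm supply the slope?** Both scores exist there, but an intercept, the slope and at least ten covariate terms leave at most 30 − 12 = 18 df. With partial correlation r and equal residual SDs (both assumed), the 95% half-width is 2.101 × √((1 − r²)/18):

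- r = 0.3: 2.101 × 0.225 = 0.47
- r = 0.5: 2.101 × 0.204 = 0.43

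A slope of 0.3 would therefore have an interval that includes zero.

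**The case against.** The strongest reply is that no bias has been shown. Patients must be opioid-naïve and having surgery at 1 to 3 levels, and microdiscectomy and chronic opioid use are excluded. Invasiveness tier, reoperation, anxiety, depression and related drugs are in both models. Together these may stand in for preoperative pain. The surgeons' selection of likely beneficiaries is one route to a difference, but that passage does not mention preoperative pain. No document says that preoperative pain predicts PACU pain, which is itself treated to a threshold. All of this stands, and it is why the point is conditional.

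A second reply is that an eleventh variable is a burden with 30 treated patients. In the simulations the extra term did not raise the SD of the estimate, but those had complete baseline scores. Missing or differently recorded control scores could change that.

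A reader might infer three stronger things that the documents do not support:

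- **The primary comparison is biased in favour of Dsuvia.** Neither the residual difference nor its sign is known.
- **The controls have no baseline score.** The plan is silent; it does not say the score is absent.
- **The power statement is wrong.** Unweighted power is about 93%. At the simulated SDs, unbiased power runs from 93% (0.54) to 79% (0.66), but the lower end comes entirely from an assumed covariate shift.

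**Conclusion.** The point holds in conditional form. It is a gap in the adjustment set and an assurance that reaches too far, not a demonstrated bias. It is more than missing detail, because the specified analysis would ignore baseline pain even where it is available for controls.

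The size cannot be determined from the documents and may be zero. The 0.5 to 0.8 point tipping range is only an illustration. It rests on an observed difference of exactly 2 points, a normal critical value, 80 controls per comparison, and SDs from assumed covariate shifts. The trial's own standard error should replace it.

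**What to change.** 1. Before any outcome comparison, check whether control charts hold a preoperative 0-10 NRS, and report availability for each control group.
2. If it is available for most controls, by a threshold fixed in advance, add baseline NRS to both the outcome and the propensity model, with a stated rule for missing scores.
3. If not, state the limitation and report the tipping-point bias for each comparison: observed difference minus critical value times the estimate's actual standard error. Do not fix a grid of baseline differences in advance, since the overturning value moves with both slope and standard error. Present any study-arm slope as illustrative only: it is imprecise and may not carry over to controls treated differently.
4. In either case, replace the unbiasedness sentence with: *consistent if at least one model is correctly specified and no confounder is omitted from both*.

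The cost is one more extraction field and a few SAP sentences, with no new patients. The downsides are control scores that may be missing or recorded differently, and one more propensity term with 30 treated patients. Making the choice before outcomes are compared keeps it from looking data-driven.

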Another recent study, by Tvetenstrand CD et al.⁶ was conducted in a hospital with ambulatory abdominal surgery patients with DSUVIA dosed 30 minutes prior to induction. A total of 47 patients were in the DSUVIA arm and 81 matched historical controls were compared. This study showed a decrease in overall IV opioid requirements and a decreased Phase 1 PACU time. No patients required naloxone for respiratory depression in either group.

Sufentanil is a drug with a rapid onset (15 min) and high potency (30 mg= morphine 5mg) (pka = 8.0 and solubility coefficient greater than 2000). It is highly bioavailable and highly lipophilic with a high therapeutic opioid index (LD50/ED50). It has a much lower Cmax compared with IV sufentanil. It reaches 70 % Cmax in 30 minutes, lasting as long as 3 hours. Based on existing outcomes data, we hypothesize that there will be a clinically significant difference in spine surgery patients as compared to the historical controls.

Purpose:

In this study we plan to examine the perioperative use of Dsuvia (sufentanil SL; FDA approval 2018) in the analgesic regimen for spine surgery, one of the most common surgeries performed in the US. Patients undergoing spinal fusion surgery often experience significant pain during the first three postoperative days⁷. Currently, no data are available for this patient population which routinely experiences moderate to severe acute pain requiring significant opioid use. We will analyze whether Dsuvia (sufentanil SL) is associated with lower pain scores, frequency of rescue

opioids, lower overall opioid consumption, PACU and hospital length of stay, and side effects of opioid use (i.e., nausea, vomiting, constipation, respiratory effects).

Hypotheses:

1. The perioperative use of Dsuvia 30 mcg SL in a prospectively recruited cohort of patients undergoing spine surgery will be associated with lower postoperative numeric rating scale pain scores (NRS; primary outcome) than observed in two historical control groups that did not receive Dsuvia: one group that received intraoperative remifentanil infusion and one that received intraoperative sufentanil infusion.

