Follow up following discharge

Prescription opioid use

Outcomes:

Primary:

Mean postoperative pain scores (PACU)

Secondary:

Mean postoperative pain scores (inpatient)

opioid consumption (MMEs, PACU and inpatient)

Frequency of opioid rescue medications given

PACU LOS (min)

hospital LOS (days)

nausea, vomiting, constipation, respiratory events

sedation level (PACU)

quality of recovery (QoR 15)

utilization of prescription opioids following discharge

As shown above, the following secondary outcomes will also be collected in the Study cohort to obtain estimates that can be used to power future randomized controlled trials: sedation level, quality of recovery (QoR-15)⁸, patient satisfaction score (satisfaction with the level of pain control, 6-point scale⁴), and utilization of prescription opioids following discharge.

Safety assessments will include adverse events (AEs) and use of concomitant medications, periodic monitoring of vital signs (blood pressure, heart rate, and respiratory rate), and continuous monitoring of oxygen saturation in the PACU.

Detailed Clinical Protocol

Preoperative:

The surgeon will approach the patient and introduce the study and one of the investigators will explain the study to the patient. The surgeon will assess subject at their visit. At this visit, the surgeons will identify any patients that may benefit from Dsuvia. The information will be provided to one of the investigators. The investigator will subsequently review their eligibility and inclusion criteria. If the subject continues to meet all the criteria, the investigator will explain the study with the patient. Thereafter the patients will be provided the consent forms for their review and a 24/7 contact number for any questions regarding this study. All patient questions will be answered and informed consent will be obtained by one of the investigators who is a licensed physician listed on the protocol. The patient will be provided contact information. A co-investigator will be available to answer

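### Mean PACU pain is scored while opioid is given for NRS >3 under a schema that can apply only to the Dsuvia arm, and the controls' PACU treatment rule is not described

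*Combined protocol and SAP*

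**What the plan says.** **Outcome.** Outcomes lists the primary as "Mean postoperative pain scores (PACU"), and Sample Size/Statistical analysis adds "The primary outcome is nurse-collected mean pain scores". On timing, Postoperative Management says "This will be obtained by using NRS scale every 15 mins up to 2 hours". No rule separates scores taken before and after an opioid dose.

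**Treatment in the same window.** Postoperative Management introduces the PACU orders with "The following opioid administration schema will be used for pain management in the PACU". First line: "patients will be ordered to receive Dsuvia 30 mcg q1 hr prn for breakthrough pain (for NRS > 3"), with doses at least 1 h apart and up to three in the PACU. Fentanyl 25-50 mcg is second line, or is used until Dsuvia can be repeated. The re-dosing rule is "If at any time the patient's NRS >3 after 20 min following an administration of either Dsuvia or fentanyl, the patient can receive a repeat"; what is repeated is fentanyl.

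**Controls.** Methods defines both historical groups as not having received Dsuvia. Their PACU drug, threshold, re-dosing interval and scoring schedule are not stated. The orders given for both groups start on transfer to the floor.

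**Hypothesis and analysis.** Hypothesis 1 is that perioperative Dsuvia "will be associated with lower postoperative numeric rating scale pain scores" than in either control group. The doubly robust analysis uses ten baseline covariates. PACU opioid consumption and rescue frequency are separate secondary outcomes under Hypothesis 2.

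**The concern.** The score that triggers treatment is also the endpoint, and the trigger rule is documented for one arm only. Mean NRS over 2 h therefore reflects the drug under test, the fentanyl given around it, and how promptly staff re-dosed. If promptness differed between the study period and the historical period, that difference enters the contrast with both control groups. It is post-baseline and coincides with group, so neither the outcome regression nor the propensity weights can separate it from Dsuvia.

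The main risk is a misattributed positive result: lower mean pain credited to Dsuvia when closer titration or more total opioid produced it. The plan records opioid use but does not say how the pain result should be read alongside it.

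**Working it through.** **1. The plan's own figure.** Inputs from Sample Size/Statistical analysis: 30 vs 80 patients, SD 2.5, difference 2, two-sided alpha 0.025.

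- SE = 2.5 × √(1/30 + 1/80) = 0.535.
- Power = Φ(2/0.535 − 2.241) = Φ(1.495) = 93.3% (92.7% with the noncentral t).
- Smallest difference with 80% power = 0.535 × (2.241 + 0.842) = 1.65 points.

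The stated power of at least 80% is met. The sample size is not in question.

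**2. Is PACU opioid use likely to be common and unequal?** The documents give no rate for this trial. The nearest figure is the matched historical-control study in Background, in mixed surgery: 48.5% of Dsuvia patients and 16.6% of controls avoided PACU opioids. So 100 − 48.5 = 51.5% and 100 − 16.6 = 83.4% received them, a gap of 31.9 percentage points.

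**3. Attenuation of a true effect.**

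*Simple version.* Assume rescue lowers a rescued patient's mean NRS by r points. A true 2-point difference then appears as 2 − 0.319r:

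| r | Observed difference | Power if SD stays 2.5 |
|---|---|---|
| 1 | 1.68 | 82% |
| 2 | 1.36 | 62% |
| 3 | 1.04 | 39% |

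*Simulation.* Assumptions: nine scores over 0-120 min, rounded and limited to 0-10; SD of untreated pain 2.5; score noise SD 0.8; control latent mean 6 or 7; 1 to 2 points of relief per dose; a dose at NRS >3 if at least 30 min have passed since the last. Both arms follow the same rule, and the true benefit is 2 points.

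- Difference at the first score, before any PACU dose: about 1.85.
- Difference in the 2-h mean: 0.9 to 1.5.
- SD of patient means: about 1.1 to 2.0, not 2.5.
- Power at 30 vs 80 with those SDs: 90-93%.

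The effect shrinks, but so does the spread, so the power losses in the table need not occur.

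**4. Bias when the rules differ.** Same model, no Dsuvia effect, control latent mean 5 to 7. Study patients are re-dosed after 30 min and controls after 60 min; the control interval is an assumption.

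- First-score difference: about 0.
- 2-h mean: 0.44 to 0.89 lower in the study arm.
- Declared significant in about 14-58% of trials using the simulated SDs, against a nominal 2.5% per comparison.

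A variant with latent mean 5, score noise SD 1 and looser control treatment gives 0.58-0.97 (control threshold NRS >5) or 0.48-0.66 (half of the triggered doses given). With SD held at 2.5, a bias of 0.5, 0.75 or 1.0 is declared significant 9.5%, 19.6% or 34.7% of the time. Exchanging the two arms' intervals reverses the sign: more prompt treatment of controls would hide a benefit by the same amount.

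**The case against.** **Mean pain with rescue allowed is a legitimate outcome.** It answers a treatment-policy question, and Hypothesis 1 speaks of association with perioperative use. PACU Dsuvia belongs to the regimen under test; strictly, only fentanyl is rescue. This stands, and is why the primary outcome should be kept.

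**Opioid use is already an outcome.** PACU MME and rescue frequency will be compared with each control group. That makes a difference visible, but does not say how it bears on Hypothesis 1.

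**Nothing shows that controls were treated differently.** The Preoperative section says routine practice applies apart from the study intervention, and floor orders use the same NRS >3 threshold for both groups. A similar PACU rule for controls is possible but not documented. Different titration therefore remains an assumption, and its direction is unknown.

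**Stronger readings that the documents do not support.** A reader might infer that rescue largely determines the scores, or that patients are titrated whenever NRS exceeds 3. No rescue rate or rescue effect is given for this trial, and the schema is permissive (as needed; can receive). A reader might also infer that a null primary result would probably mean that rescue worked, or that the trial can say nothing about pain. The simulated power of 90-93% under equal titration does not support the first. The second goes too far, because the regimen-level comparison remains meaningful.

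**Conclusion.** The concern holds as one of interpretation and possible bias, not of sample size. Outcome and NRS-triggered treatment share one window, the schema can describe only the study arm, and baseline adjustment cannot remove a difference in PACU treatment rules. If controls were re-dosed at 60 min rather than 30 min, the false benefit is about 0.4-0.9 point, up to nearly half of the 2-point target. That figure rests on the assumed intervals, 1-2 points of relief per dose and latent means of 5-7. The documents fix none of these, so it shows a plausible size and does not estimate the actual bias. The plan should deal with this before the data are analysed.

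**What to change.** Keep the primary outcome and clinical care unchanged, and add to Sample Size/Statistical analysis:

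1. **Claim.** State that Hypothesis 1 compares the whole Dsuvia-based PACU regimen, including its fentanyl schema, with historical practice. Word the conclusion that way.
2. **Supportive analysis.** Prespecify the first PACU NRS before any PACU opioid, in all three groups, with the same doubly robust model. State how patients with no such score are handled.
3. **Joint reading.** Report and interpret the primary result together with PACU MME, counting Dsuvia. State the conversion and whether the tablet given in the operating room counts. Background's only equivalence is in mg while the tablet is in mcg, so those passages must be reconciled first. If PACU MME is higher in the study arm, or the first score shows no difference, say so openly beside any statement that Dsuvia itself lowered pain.
4. **Control data.** Extract control PACU opioid times and NRS scoring times from the chart, and tabulate them against the study arm to show whether titration was comparable.

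A combined pain-and-opioid rank score is optional and exploratory, since its equal weighting is a matter of choice.

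**Cost.** Analysis-plan wording, one supportive analysis and chart extraction. The claim becomes narrower, and control chart data may be incomplete. The first score may precede the full effect of the operating-room tablet (Background gives onset at 15 min and 70% of Cmax at 30 min) and precedes any PACU tablet. It should therefore be supportive, not a condition for success.
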